Trial design and methods:	Individual qualitative interviews to develop the intervention in Phase 1. Open uncontrolled feasibility study assessing the acceptability and feasibility of ACT for treatment-resistant GAD in older people using quantitative and qualitative methods in Phase 2. Primary outcome measures will be acceptability (session engagement and satisfaction with therapy) and feasibility (recruitment and retention). Individual qualitative interviews with participants and therapists will further assess acceptability and feasibility.
Trial duration per	6 months in Phase 1 and 20 weeks in Phase 2
Estimated total trial	24 months
Planned trial sites:	Multi-site
Total number of participants planned:	15 in Phase 1 and 40 in Phase 2
Main inclusion/exclusion	Inclusion criteria:
criteria:	 Older people aged 65+ with a primary diagnosis of GAD as determined by the MINI International Neuropsychiatric Interview (Sheehan et al., 1998) and the Structured Clinical Interview for DSM-IV Axis II Disorders (First et al., 1995, 1997); Failed to respond to treatment in Steps 1-3 of the stepped care approach for GAD; Living in the community; Able to provide informed, written consent; Sufficient understanding of English to enable them to engage in ACT and complete patient-reported outcome measures; In Phase 2 only: Have not participated in qualitative interviews in Phase 1 of the project.
	Exclusion criteria:
	 Diagnosis of dementia; Standardised Mini-Mental State Examination (Molloy et al., 1991) score of <25; Currently receiving ongoing psychotherapy or who are unwilling to refrain from engaging in other forms of psychotherapy during the receipt of ACT; Suicidal ideation with active intent for whom an inpatient admission would be more appropriate; Other medical or psychosocial factors that could compromise full study participation such as imminently life-limiting illness or severe sensory deficits (e.g. blindness); Intellectual disabilities.
Statistical methodology and analysis:	In Phase 1 and 2, qualitative data will be transcribed verbatim and analysed iteratively using thematic analysis In Phase 2, binary and other categorical measures will be summarised using frequencies and percentages, and continuous measures using means and standard deviations (or medians and interquartile ranges for very skewed distributions). Change in patient-reported outcome measures between 0 and 20 weeks will be estimated using

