Following development of the intervention, further individual qualitative interviews with the same set of 15 older people with GAD who completed the initial interviews will be conducted. Again, participants will be recruited from London and Oxfordshire to obtain a variety of service user perspectives. Interviews will examine: the acceptability and perceived value of the different components of the intervention; the practicalities of the intervention (e.g. number and frequency of sessions, settings, etc); and ways of optimising engagement (e.g. provision of mid-week telephone calls, peer mentors to provide support during therapy, etc). The feasibility of conducting ecological momentary assessment, a method of collecting real time data via smartphones, phone calls and emails that is more reliable and sensitive to change than paper-and-pencil measures will also be explored. Traditional paper-and-pencil measures typically enquire about mood over an extended period of time (e.g. the past week). Ecological momentary assessment enquires about mood in the present moment, and so, as well as being more appropriate for older people who may find it difficult to recollect how they have been feeling in the past week, may fit well with the core clinical processes addressed in ACT (e.g. mindful awareness of emotional experiences in the present moment). However, this assessment approach may not be feasible to complete if older people have limited access to smartphones or PCs, or if completion via phone calls in the absence of smartphone or PC access is perceived as burdensome. Two interested service users from qualitative interviews conducted at the beginning of Phase 1 will be invited to contribute to the analysis of these data. Following this, the intervention will be modified in collaboration with the Project Service User Advisory Group. Specifically, they will be invited to comment on qualitative interview data, and review the intervention and any proposed revisions before it is implemented in Phase 2.

Phase 2: Evaluation of the intervention

In Phase 2, the acceptability and feasibility of the intervention will be assessed within an open uncontrolled feasibility study. ACT will be delivered:

i) In an anticipated 16 1-hour sessions;

ii) With a phased ending such that sessions will be weekly for the first 14 weeks and every 2-3 weeks thereafter as some older people experience difficulties when therapy ends abruptly;

- iii) Individually rather than in groups;

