8.5 Definition of end of trial

The expected duration of the study is 20 months from recruitment of the first participant. The end of the study is the date of the last follow up visit of the last participant.

9 Recording and reporting of adverse events

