Appendix 1 – Flowchart of phases in the FACTOID study.

Phase 1: Manual development	Conduct qualitative interviews with an estimated 15 older people with GAD. Discuss what components should be included in an intervention for older people with treatment-resistant GAD, and how it can be tailored to this population. Discuss with clinical experts in the field. Conduct nationwide online and paper-based survey of clinicians' and service users' views of what constitutes usual care for older people with treatment-resistant GAD. Develop and manualise an ACT intervention for older people with treatment-resistant GAD.
	Conduct qualitative interviews with the same 15 older people with GAD (as above) to discuss the acceptability of the intervention. Make modifications to it in collaboration with the Project Service User Advisory Group.
đị	Begin recruitment via self-referral and GP list searches and from GPs and Improving Access to Psychological Therapies services in primary care and Community Mental Health Teams for older people in secondary care.
llow.	
tion & fo	Identify and approach potential participants about the study ($n = 131$).
ıt, interver	Decline to participate (n = 46).
Inrolmer	Assess potential participants for eligibility ($n = 85$).
e 2: H	
Phas	Obtain consent to participate from eligible participants. Complete pre-intervention assessment (0 weeks; n = 40).
	Complete post-intervention assessment (20 weeks; n = 35). Conduct qualitative interviews with an estimated 15 older people and all therapists to further assess the acceptability of our manual.
ysis & ion	Complete data analysis (n = 40).
Analy	
Phase 3: . dissem	Make modifications to the manual in collaboration with the Project Service User Advisory Group. Write up and disseminate results.

Appendi x	2 –	Project	timetable	and	milestones
-----------	-----	---------	-----------	-----	------------

Date	Activity	Milestone(s)
Months -6-0: Nov	Pre-orientation	Apply for ethical and research governance approvals. Place advert for research
2016-Apr 2017		assistant with date of interview. Devise 4-day training workshop. Identify
		therapists.
Months 1-3: May-	Orientation & Phase	Interview and appoint research assistant. Purchase equipment. Develop procedures
Jul 2017	1: Develop manual	and policies for the conduct of the study. Set up Project Development Group,
		Project Management Group and Study Steering Committee. Conduct first wave of

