		qualitative interviews with service users. Discuss manual development with
		experts. Conduct 4-day training workshop on ACT with therapists. Set up online-
		and paper-based nationwide survey of what constitutes usual care for treatment-
		resistant GAD in older people.
Months 4-6: Aug-	Phase 1: Develop	Analyse qualitative data. Develop manual. Conduct second wave of qualitative
Oct 2017	manual	interviews with service users. Make modifications to the intervention based on
		interview data, in partnership with the Project Service User Advisory Group.
		Devise 1-day training workshop on applying ACT to older people with treatment-
		resistant GAD.
Months 7-9: Nov	Phase 2: Feasibility	Conduct 1-day training workshop on applying ACT to older people with treatment-
2017-Jan 2018	study	resistant GAD with therapists. Recruit participants at a rate of 4 participants per
		month. Deliver ACT.
Months 10-20:	Phase 2: Feasibility	Recruit participants (finish by end of Aug 2018). Deliver ACT intervention (finish
Feb-Dec 2018	study	by end of Dec 2018). Collect outcome measures and conduct qualitative interviews
		with participants and therapists.
Month 21: Jan	Phase 3: Data	Clean and analyse quantitative and qualitative data. Rate ACT tapes.
2019	analysis	
Months 22-24:	Phase 3: Write up &	Prepare final report. Write draft of paper. Make final modifications to the
Feb-Apr 2019	revise manual	intervention with the Project Service User Advisory Group. Disseminate findings.
		Prepare application for funding of a substantive trial.

Months	-6-0	1-3	4-6	7-9	10-12	13-15	16-18	19-21	22-24
Dates	Nov 2016-Apr 2017	May-Jul 2017	Aug-Oct 2017	Nov 2017-Jan 2018	Feb-Apr 2018	May-Jul 2018	Aug-Oct 2018	Nov 2018-Jan 2019	Feb-Apr 2019
Pre-									
orientation									
Orientation									
Develop									
intervention									
Conduct									
survey									
Recruitment									
Deliver ACT									
Data analysis									
Write up &									
disseminate									
results									
Revise									
intervention									

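### Appendix 2 leaves 17.4 weeks between the close of recruitment and the end of outcome collection, too short for the last participants' 20-week assessment

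*Protocol*

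**What the plan says.** The milestone table in Appendix 2 gives Months 10-20 (February to December 2018) one row. It reads "Recruit participants (finish by end of Aug 2018). Deliver ACT intervention", with that delivery to finish "by end of Dec 2018). Collect outcome measures and conduct qualitative interviews". The next row, Month 21 (January 2019), holds only this work: "Clean and analyse quantitative and qualitative data. Rate ACT tapes".

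The follow-up length is stated in several places. The Summary gives the participant's duration as "6 months in Phase 1 and 20 weeks in Phase 2". Appendix 1 has "Complete post-intervention assessment (20 weeks; n = 35", counted from a pre-intervention assessment at 0 weeks. Sections 8.3 and 11.2 place the patient-reported outcomes at 0 and 20 weeks. Section 11.1 judges retention, one of the four success criteria, by attendance at the final follow-up assessment, with a threshold of 60%.

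For therapy, section 8.2.1 anticipates 16 sessions and says "sessions will be weekly for the first 14 weeks and every 2-3 weeks thereafter".

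Section 8.5 says "The expected duration of the study is 20 months from recruitment of the first participant", and defines the end of the study as the last participant's last follow-up visit.

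**The concern.** The calendar in Appendix 2 and the 20-week follow-up cannot both hold for people enrolled at the end of the recruitment period. If the team works to the calendar, those people are assessed early, possibly before therapy ends, or are not assessed before analysis begins.

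One visit carries much of the study. It determines retention. Under Appendix 4 it also supplies the satisfaction scale (another success criterion) and every post-treatment patient-reported outcome. The 20-week service-use data for costing in section 11.5.6 come from it too. Retention and variance estimates from this study are meant to inform a larger trial, so a follow-up missed because of the calendar would be a design artefact that looks like participant behaviour.

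**Working it through.** **Inputs**
- Recruitment closes 31 August 2018 (Appendix 2).
- ACT delivery ends 31 December 2018. Outcome collection is in the row ending the same month (Appendix 2).
- Assessment is 20 weeks after the 0-week assessment (Appendix 1; sections 8.3 and 11.2). The 0-week date is taken as the enrolment date; a later baseline would widen the gap.
- Visit window is given as an example of plus or minus 2 weeks (Appendix 4).
- Recruitment is 4 per month for 10 months (section 11.4, Appendix 2).

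**The plan's own figures.** November 2017 to August 2018 is 10 months, and 10 × 4 = 40, as stated. In section 11.3, 35 / (1 − 0.125) = 40, also as stated.

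**Time available to the last enrollee.** 31 August to 31 December 2018 = 30 + 31 + 30 + 31 = 122 days, and 122 / 7 = 17.4 weeks. This is 18 days (2.6 weeks) short of 20 weeks (140 days) and 4 days short of 18 weeks (126 days).

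**Due dates and latest enrolment**

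| Assessment at | Due if enrolled 31 Aug 2018 | Latest enrolment to be seen by 31 Dec 2018 |
|---|---|---|
| Week 18 (early edge) | 4 Jan 2019 | 27 Aug 2018 |
| Week 20 | 18 Jan 2019 | 13 Aug 2018 |
| Week 22 (late edge) | 1 Feb 2019 | 30 Jul 2018 |

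**Number affected.** The recruitment period has 304 days, so the even rate is 40 / 304 per day.
- Enrolled 14-31 August: 18 days × 40 / 304 = 2.4 people (18 / 31 × 4 = 2.3 at the monthly rate).
- Enrolled 28-31 August, if the whole early window is used: 4 days × 40 / 304 = 0.5 person.

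**Effect on the retention criterion.** The threshold is 0.60 × 40 = 24. Suppose 2 people were lost on top of the 5 already allowed for: 40 − 5 − 2 = 33, and 33 / 40 = 82.5%. With 3 it is 32 / 40 = 80%. Both are well above 60%.

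**Therapy span.** With session 1 at week 0, session 14 falls at week 13, and two further sessions at 2-3 week intervals put the last at 13 + 4 = 17 to 13 + 6 = 19 weeks. With session 1 a week later, the last falls at 18 to 20 weeks. Only the shortest case fits within 17.4 weeks.

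**Section 8.5.** Twenty months from the start of May 2017 (Phase 1) ends at 31 December 2018. A first recruitment on 18 May 2017 would put the end at 18 January 2019. Twenty months from the start of November 2017 (Phase 2) ends at 30 June 2019, after the project closes in April 2019. The section does not say which phase's first participant starts the clock.

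**The case against.** The strongest reply is that nothing in the protocol obliges anyone to lose these data. Section 8.5 ends the study at the last follow-up visit, and no passage sets a data cut-off or counts late enrollees as lost. Only recruitment and ACT delivery carry an explicit finish date. The end of outcome collection is inferred from its row and from January being given to analysis; the shading of the chart below the table could not be read for this check. On the most natural counting, section 8.5 itself could stretch to 18 January 2019 or beyond. All of this stands, and it makes the problem a conflict between passages and not a rule that discards data. Section 8.3 also allows telephone collection at 20 weeks, but that changes the mode of the visit and not its due date.

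Three stronger readings are tempting, and the documents do not support them.
- A reader might count about 4 people as lost, by including everyone enrolled after 30 July. Those enrolled from 31 July to 13 August still reach week 20 by 31 December; they only lose the late edge of the window.
- A reader might conclude that the therapy schedule can never fit. With session 1 at enrolment and the shorter spacing it ends at week 17, and 16 sessions is only an anticipated number.
- A reader might infer that the window lets the assessment precede the last session. The plus or minus 2 weeks is only an example, and Appendix 4 places the follow-up visit after the final intervention visits.

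**Conclusion.** The point holds as a small but real date conflict. The timetable allows 17.4 weeks where the follow-up needs 20, and the example early window does not close the gap. The number affected is about 2 of 40, or about 0.5 if the early window is fully used. This assumes that recruitment runs evenly to its last day, that baseline coincides with enrolment, and that outcome collection stops with its row in December 2018.

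It might be inferred that retention would fail or that the study's success is in doubt. The figures do not support that: the criterion needs 24 of 40, and even adding every affected person to the planned losses leaves about 32 or 33. What is at stake is the completeness and timing of follow-up for a few late participants, and the accuracy of the estimates passed to the future trial.

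**What to change.** In Appendix 2, extend Phase 2 outcome collection to at least 18 January 2019 (31 August 2018 + 20 weeks), or to 1 February 2019 (+ 22 weeks) if a +2-week window is kept. Start the quantitative analysis after that date. Make section 8.5 agree by naming which phase's first participant starts the 20 months, or by giving a calendar date. The ACT finish date in Appendix 2 and the session schedule in section 8.2.1 also need to be reconciled; that is for the investigators to settle.

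The cost is 18 to 32 days, roughly 2.5 to 4.5 weeks, out of the four months (January to April 2019) set aside for analysis and write-up. Qualitative analysis and tape rating for earlier participants can proceed meanwhile. No extra participants are needed and the 24-month total is unchanged. Closing recruitment by 13 August 2018 instead would also remove the conflict over the 20-week visit, but it would shorten the 10-month period on which the recruitment criterion is judged.

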Appendix 4 – Schedule of assessments

	Phase 1: Screening	Phase 1 develo	: Manual pment	Phase 2: Screening & baseline Ax		Phase 2: Intervention						Phase 2: Follow-up Ax	
Visit No	1	2	3	1	2-3	4-5	6-7	8-9	10-11	12-13	14-15	16-17	18
Day(s)	1	2	3	1	1-2	3-4	5-6	7-8	9-10	11-12	13-14	15-16	1
Window of flexibility for visits	N/A	e.g. +/- 2 weeks	e.g. +/- 2 weeks	N/A	e.g. +/- 2 weeks	e.g. +/- 2 weeks	e.g. +/- 2 weeks	e.g. +/- 2 weeks	e.g. +/- 2 weeks	e.g. +/- 2 weeks	e.g. +/- 2 weeks	e.g. +/- 2 weeks	e.g. +/- 2 weeks
Informed consent	Х			Х									
GAD-7	Х			Х									
MINI	Х			Х									
SCID	Х			Х									
SMMSE	Х			Х									
Eligibility confirmation	Х			Х									
GAI				Х									Х
PWSQ				Х									Х
GDS-15				Х									Х
EQ-5D-5L				Х									Х
CSRI				Х									Х
AAQ-II				Х									Х
STTS-R													Х
CEQ					Х								
Qualitative interview		Х	Х										Х
Intervention					ACT+	ACT+	ACT+	ACT+	ACT+	ACT+	ACT+	ACT+	
AE review	X			X	Х	Х	Х	Х	Х	Х	Х	Х	X

Note: AAQ-II = Acceptance and Action Questionnaire-II; ACT+ = Acceptance and Commitment Therapy plus usual care; AE = adverse events; Ax = assessment; CEQ = Credibility/Expectancy Questionnaire; CSRI = Client Service Receipt Inventory; GAD-7 = Generalized Anxiety Disorder-7; GAI = Geriatric Anxiety Inventory; GDS-15 = Geriatric Depression Scale-15; MINI = MINI International Neuropsychiatric Interview; PSWQ = Penn State Worry Questionnaire; SCID = Structured Clinical Interview for DSM-IV Axis II Disorders; SMMSE = Standardised Mini-Mental State Examination; STTS-R = Satisfaction with Therapy and Therapist Scale-Revised.
